1.1.2 Clinical evidence

Observational clinical data supporting the rationale to investigate emapalumab in GF are derived from pediatric studies in HLH (NI-0501-04 and NI-0501-05), emapalumab compassionate use cases (data in Sponsor files), and a separate prospective data set of pediatric patients with varying underlying diseases who received HSCT (6).

[figure not shown]
Data from HLH patients undergoing HSCT (n=26) in studies NI-0501-04 and NI-0501-05, and after compassionate use of emapalumab, show a systematic and specific elevation of IFN γ prior to GF (primary and secondary), and in particular an elevation of CXCL9. CXCL9 is almost exclusively produced by activation of the IFN γ receptor and therefore a good surrogate marker of IFN γ activity. An elevation of CXCL9 above 300 pg/mL (value obtained by measuring CXCL9 with Meso Scale Discovery [MSD] assay) was observed several days prior to any other evidence of primary GF and a few days before (or concomitantly) to secondary GF. An elevation of CXCL9 was shown to predict GF with an approximately 86% positive predictive value (PPV) (i.e. risk of GF in patients positive for the marker) and 90% to 100% sensitivity (very low or no false negatives).

In conclusion, during the post-transplant period, total IFN γ levels (and even more specifically CXCL9 levels) were elevated in patients experiencing GF. On the contrary, low levels of CXCL9 were observed in patients that didn't experience GF. Given that an elevation of CXCL9 above 300 pg/mL was systematically observed prior to GF post HSCT, CXCL9 can be considered a good predictor of GF.

A separate prospective data set (6), including 15 pediatric patients with various underlying diseases who received HSCT and experienced GF, and 15 matching pediatric controls who did not experience, has shown the same and highly predictive IFN γ signature of GF (Figure 1).

CXCL9 levels by day 3 post-transplant predicted GF with 88.89% sensitivity based on a cutoff of 274.5 pg/mL. Additionally, CXCL9 levels observed prior to GF in patients without HLH were consistent with the levels observed in HLH patients.

Figure 1: CXCL9 Levels Increase from Day 3 Post HSCT in GF patients and similarly for HLH and non-HLH Patients

*: p<0.05;

** : p<0.01; ***: p<0.001

Left figure (with HLH patients): n=30, right figure (without HLH patients): n= 26

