		Criteria to start emapalumab treatment for prevention of primary GF: ANC < 500/μL + CXCL9 above threshold	Criteria to start emapalumab treatment for prevention of secondary GF: Signs of secondary GF⁴ + CXCL9 above threshold	
		↓ ↓ ↓ ↓	↓ ↓ ↓ ↓	
		Treatment must start within 12 hours from CXCL9 sample collection time TREATMENT PERIOD (Up to engraftment ⁵ or maximum 15 doses)	Treatment must start within 12 hours from CXCL9 sample collection time TREATMENT PERIOD (optional) (Up to engraftment ⁵ or maximum 15 doses)	

¹Extended monitoring for secondary GF (sGF) starts as soon as ANC equal or above 500 cells/μL during the monitoring period.
 
²For patients treated with emapalumab: the follow-up period starts one week after last study drug administration (or EoT) and consists of 6 visits and 3 phone calls at 1, 2 and 3 years after HSCT.
 
³For patients who have not received emapalumab: the follow-up period will start one week after the last day in the monitoring or extended monitoring periods and will last 3 years from HSCT and will consist of phone calls at 6 months, 1, 2 and 3 years after HSCT.
 
⁴Donor chimerism drop of at least 10% for 2 consecutive measurements and/or ANC below 500 cells/μL and/or thrombocytopenia below 30000/μL not explained by any other reason than potential graft rejection.
 
⁵Engraftment for primary GF is defined as ANC \geq 500 cells/μL for 3 consecutive measures and donor chimerism above 60%. Engraftment for secondary GF is defined as ANC \geq 500 cells/μL for 3 consecutive measures and 2 consecutive measures of donor chimerism above 60% or 7 days of platelets above 20000 cells/μL without transfusion.
				

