3.2 Study design rationale

This study is designed as an open-label, single arm, proof of concept study in order to determine the appropriate emapalumab dosing regimen neutralizing IFN γ in patients at risk of GF prior to initiating a pivotal study.

An open label, single arm design is considered appropriate given the life-threatening condition of the patient population and due to the early stage of development of emapalumab in this indication. The proposed treatment strategy is not an alternative to current treatments, therefore patients will receive the same standard of care as if they were not enrolled in the study.

Patients receiving HSCT at high risk of GF will be included in the study to ensure patients with highest unmet need are included. Only patients presenting CXCL9 levels above a defined threshold and an ANC below 500 cells/ μ L will be eligible to receive emapalumab treatment for primary GF. Patients with CXCL9 above threshold will also be eligible to receive emapalumab based on treating physician's decision in case of signs of secondary graft failure (i.e. donor chimerism drop of at least 10% for 2 consecutive measurements and/or ANC below 500

cells/ μL and/or thrombocytopenia below 30000/ μL not explained by any other reason than potential graft rejection) during the extended monitoring period.

CXCL9 elevation is observed several days prior to any clinical signs of primary GF and provides the opportunity of a biomarker driven pre-emptive treatment approach and to initiate early treatment to inhibit the deleterious activity of IFN γ on the graft. In case of secondary GF, preliminary observations have shown an elevation of CXCL9, a few days before GF or concomitantly (see section 1.1.2 and IB). This preliminarily observed difference of CXCL9 elevation time prior to GF justifies the need to consider pre-emptive treatment of secondary GF as optional based on medical judgment.

For the above mentioned reasons, each study cohort completion is based on the recruitment of the required number of evaluable patients treated for primary GF (see sample size section 12.1). Given that similar PK/PD profile of emapalumab is expected in patients treated to pre-empt primary and secondary GF, data obtained in the secondary GF patients may be used to inform dose decision for the subsequent cohorts.

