3.4.3 Monitoring and extended monitoring periods

Assessments to be performed during the monitoring periods are presented in the schedule of assessment (Table 5a and Table 5b).

See Table 2 and Table 3 for details on the transition from monitoring to extended monitoring, treatment and follow up in case of ANC < 500/ μ L (Table 2) and \geq 500 cells/ μ L (Table 3) during the monitoring period.

CXCL9 measurements will be performed by means of a validated assay on a device provided to the sites by Sobi AG. The exact CXCL9 threshold for treatment initiation will be provided in the CXCL9 assay laboratory manual.

Monitoring period

The monitoring period will start from the day after the HSCT (day 1) and will last until ANC is \geq 500 cells/ μ L or maximum until monitoring day 42 \pm 1, whichever comes first. During the monitoring period, CXCL9 and ANC measurements will be performed daily from day 1 up to day 7, every other day starting from day 9 until day 21 and every 3 days (\pm 1) starting from day 24 until day 42.

- If CXCL9 is measured above threshold and ANC is below 500 cells/ μ L, patients will enter the treatment period.
- If CXCL9 is measured below threshold and ANC is below 500 cells/ μ L, patients will continue the monitoring period until day 42 \pm 1 or until a second HSCT is planned.
- As soon as the ANC will be \geq 500 cells/ μ L during the monitoring period, patients will move to the extended monitoring period for secondary GF (sGF).

Extended monitoring period

The extended monitoring period will start as soon as the ANC will be equal or above 500 cells/ μ L during the monitoring period and will last maximum 98 \pm 3 days.

During the extended monitoring, CXCL9 and ANC measurements will be performed weekly up to day 98 \pm 3 days. In case of signs of sGF outside of the weekly visits, the patient should attend for an unscheduled visit and the assessments foreseen in the extended monitoring period visit should be performed to assess eligibility for treatment.

- If CXCL9 is measured above threshold and there are signs of sGF (i.e. donor chimerism drop of at least 10% for 2 consecutive measurements and/or ANC below 500 cells/ μ L and/or thrombocytopenia below 30000/ μ L not explained by any other reason than potential graft rejection), patients may optionally enter the treatment period, if the investigator will consider pre-emptive treatment with emapalumab the best option for the patient.

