4.1 Inclusion criteria

1. Informed consent form signed by the patient (as required by law) or by the patient's legally authorized representative(s) with the assent of patients who are legally capable of providing it, as applicable.
2. Recipients of allogeneic HSCT and at high risk of GF, based on at least one of the following criteria:
 - Receiving reduced intensity conditioning (RIC) or non-myeloablative (NMA) conditioning, combined with a non-malignant disease or with a graft from Bone Marrow (BM).
 - *Ex vivo* T cell depleted graft.
 - Graft from mismatched unrelated or haploidentical donor.
 - Graft from Umbilical Cord Blood (UCB).
3. Patients requiring allo-HSCT with the following underlying diseases:
 - Malignant disease with high risk of GF, i.e. Acute Myeloid Leukemia (AML) and Acute Lymphoblastic Leukemia (ALL), with primary induction failure, second partial remission or relapse; Chronic Myeloid Leukemia (CML) in blastic phase (circulating blast or blast above 5% in biopsy); Non Hodgkin and Hodgkin Lymphoma and multiple myeloma with primary induction failure, second partial remission or relapse; myelodysplastic syndromes (MDS) and myeloproliferative disorders (MPD) with splenomegaly; myelofibrosis with portal hypertension pre-transplant; MDS/MPD overlap syndromes.
 - Non-malignant hematological diseases (e.g. autoimmune and metabolic disorders, aplastic anemia, Sickle cell anemia, Fanconi anemia, Diamond-Blackfan anemia, thalassemia, osteopetrosis, Wiskott-Aldrich syndrome, severe combined immunodeficiency, Hemophagocytic lymphohistiocytosis and other immunoregulatory disorders).
4. Male and female patients.
5. Children aged at least 1 year and adults. Once the appropriate dose has been determined in one of the three cohorts and safety has been assessed by the IDMC, children less than 1 year old may be included in the study.
6. Females of child-bearing potential, defined as all women physiologically capable of becoming pregnant, require the use of highly effective contraceptive measures from screening until 6 months after the last study drug administration.

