8 VISIT SCHEDULE AND STUDY ASSESSMENTS

The visit schedule and the study assessments for patients of **weight ≥ 30 kg** are described in Table 5a (Screening, HSCT, monitoring and extended monitoring periods), Table 6a (Treatment period), Table 7a (Follow-up period, unscheduled visit and withdrawal visit).

The visit schedule and the study assessments for patients of **weight < 30 kg** are described in Table 5b (Screening, HSCT, monitoring and extended monitoring periods), Table 6b (Treatment period), Table 7b (Follow-up period, unscheduled visit and withdrawal visit). Some assessments are not performed in patients of **weight < 15 kg** and these are indicated with an (*) in the assessment schedule.

Visits must occur on the designated day with allowed window as indicated. The same assessment schedule is foreseen for Cohort 1, 2 and 3.

The assessments that are mandatory during a visit are marked with an X. Optional assessment to be performed based on medical judgment are marked with an (X).

Table 5a: Schedule of assessments for Screening, HSCT, monitoring and extended monitoring (cohort 1, 2 and 3) – Patients ≥ 30 kg

PERIOD (Duration)	SCREENING (Up to 13 days)	HSCT ¹ (1 day)	MONITORING (Up to 42 ±1 days)	EXTENDED MONITORING (Up to 98 ±3 days)	
VISITS Days ± visit window	SD -21 to SD-8	D0	MD1, MD2, MD3, MD4, MD5, MD6, MD7 MD9, MD11, MD13, MD15, MD17, MD19, MD21, MD24±1, MD27±1, MD30±1, MD33±1, MD36±1, MD39±1, MD42 ±1	Visits every 7±1 days First EM visit is 7±1 days from the last day in the monitoring period (patient transition to EM period as soon as ANC ≥500 in the monitoring)	
Demographics and baseline characteristics	Informed Consent	X			
	Demographics	X			
	Relevant medical history and previous treatments	X			
	Donor and graft characteristics		X		
Clinical Assessments	Stratification by underlying disease (malignant/non-malignant)	X			
	Review of inclusion/exclusion criteria ²	X	X		
	Assess eligibility to emapalumab treatment			X	
	Height	X			
	Weight	X	X		
	Vital Signs (BP, HR, body temperature)	X	X	X	
	Chest X-Ray	X		Anytime a pulmonary infection is suspected	
	12-Lead ECG	X			
	Physical Examination	X	X	As clinically indicated	
Occurrence of GvHD and/or engraftment syndrome, graft failure, graft rejection			X		
Laboratory procedures	Search for infections ³		X ³	Anytime an infection is suspected	
	TB testing ²	X		Anytime an infection is suspected	
	Serum pregnancy test	X			
	Urine pregnancy test		X	MD30	Every 4 weeks (from last pregnancy test)

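### Section 3.4.3 ends primary graft-failure monitoring on the first ANC of 500 or more, with no prior fall below 500, no confirming value and no route back

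*Combined protocol and SAP*

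**What the plan says.** **Trigger.** Monitoring for primary graft failure (GF) starts on day 1. At the first ANC of 500 or more, "patients will move to the extended monitoring period for secondary GF (sGF" (section 3.4.3). The synopsis, section 3.2, Table 1 footnote 1 and Table 3 repeat this. Table 3 leads on only to treatment or follow-up.

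**Sampling.** In monitoring, ANC and CXCL9 are measured daily to day 7, every second day from day 9 to day 21, then every third day to day 42. After the move, "During the extended monitoring, CXCL9 and ANC measurements will be performed weekly up to day 98". Tables 5a and 5b add: "First EM visit is 7±1 days from the last day in the monitoring period".

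**Treatment.** In monitoring, a patient with CXCL9 above threshold and ANC below 500 enters treatment. In extended monitoring, a patient with CXCL9 above threshold and a sign of secondary GF "patients may optionally enter the treatment period", at the investigator's discretion. The Table 1 column for that period is headed "Criteria to start emapalumab treatment for prevention of secondary GF".

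**Definitions.** Section 1.1 separates primary from secondary GF by whether engraftment first occurred. For treated patients in the primary setting, section 3.4.4 accepts engraftment on three consecutive ANC values of 500 or more plus donor chimerism above 60%. It adds a preference for three ANC values drawn 1 or 2 days apart.

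**Eligibility.** One qualifying category in section 4.1 is "Receiving reduced intensity conditioning (RIC) or non-myeloablative (NMA) conditioning", with a non-malignant disease or a bone marrow graft. Neither 4.1 nor 4.2 contains an ANC criterion.

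**Analysis.** The All evaluable population (section 12.4) holds only patients treated for primary GF. Section 12.2 gives decision guidance after 4 and 7 such patients.

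**The concern.** One count stands in for initial engraftment. Two kinds of patient can meet it without having engrafted: one whose neutrophils have not yet fallen after conditioning, and one with a brief rise. Three things then change.

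- **Scheduled sampling becomes weekly.** The strategy depends on lead time: "CXCL9 elevation is observed several days prior to any clinical signs of primary GF" (section 3.2), and in the paediatric data set of section 1.1.2, "CXCL9 levels by day 3 post-transplant predicted GF with 88.89% sensitivity". A weekly interval can use up that lead.
- **Treatment becomes optional.** Section 3.2 justifies this by CXCL9 rising only shortly before, or together with, secondary GF. That reason does not fit a patient who never engrafted.
- **The label changes.** A treated patient counts as secondary GF and leaves the set used for cohort completion and interim guidance.

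**Working it through.** **1. Does the text support the reading?** Section 3.4.3 and Tables 1, 2, 3, 5a and 5b were compared. None asks for a second value or an earlier ANC below 500, and none describes a return to primary monitoring. Read literally, an ANC still at 500 or more on day 1 ends primary monitoring on day 1.

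**2. Scheduled samples up to day 42.** The monitoring days are 1–7 (7 samples), 9–21 in steps of 2 (7) and 24–42 in steps of 3 (7), so 21 in all. After a trigger on day T, extended visits fall on T+7, T+14 and so on; the range uses 8-day and 6-day spacing.

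| Trigger day T | Left on monitoring schedule | Left on extended schedule (range) |
|---|---|---|
| 1 | 20 | 5 (5–6) |
| 11 | 12 | 4 (3–5) |
| 15 | 10 | 3 (3–4) |
| 21 | 7 | 3 (2–3) |

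**3. How much of that difference counts?** Treatment for primary GF also needs ANC below 500, so a sample taken while ANC is 500 or more could not have started it. Only samples after the fall are lost opportunities. Take T = 1 and assume ANC falls below 500 on day f and stays there. The monitoring samples from day f to day 7 number 8 − f: 6, 5, 4, 3, 2 and 1 for f = 2 to 7. For f up to 6, patients under 15 kg have one fewer, because day 6 is skipped. The extended schedule has none before day 8 (±1). If ANC never falls, none of the 20 − 5 = 15 missing samples could have triggered treatment.

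**4. A transient later rise.** For T = 11, the samples on days 13, 15 and 17 drop out before the day-18 visit. For T = 15, days 17, 19 and 21 drop out before day 22. For T = 21, days 24 and 27 drop out before day 28.

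**5. Time to two further scheduled ANC values.** On the monitoring schedule this takes 2 days (T = 1–5), 3–4 days (T = 6–17) or 5–6 days (T = 19–36). On the extended schedule it takes 2 × 6 = 12 to 2 × 8 = 16 days.

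**6. Recruitment.** The plan's 15 to 40 monitored patients per cohort roughly reproduces: 4/0.30 = 13.3, so 14, and 4/0.10 = 40. Suppose a share m of would-be primary-GF patients were re-routed, and the 10–30% rate does not already reflect the rule. The number becomes 4/(rate × (1 − m)). For m = 10%, 20% and 30% this gives 45, 50 and 58 at the 10% rate, and 15, 17 and 20 at the 30% rate. The value of m is an assumption; the documents give none.

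**The case against.** The case against has real weight.

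- **The drug is still available.** In extended monitoring, ANC below 500 with CXCL9 above threshold is itself a treatment criterion, with the same 12-hour start and the same dose (section 5.4). Chimerism and platelet signs also qualify. This stands: what changes is scheduled frequency, discretion and label.
- **Unscheduled visits are foreseen** for signs of secondary GF. This stands in part. A CXCL9 rise alone is not a listed sign. After such a visit the regular schedule resumes (section 3.4.6), and no repeat frequency is set. Below 30 kg, chimerism is measured only when clinically indicated.
- **Section 3.4.4 prefers three ANC values.** It does, but under Treatment Period and only as a preference. Section 3.4.3 does not refer to it, and it does not address a count that has not yet fallen.
- **Section 3.2 speaks of ANC increase after transplant**, so an exit on day 1 is probably not intended. That is likely true, but sites follow the rule as written.
- **Later rises are probably uncommon**, because a patient with high CXCL9 and ANC below 500 at an earlier sample would generally already be on treatment. This stands.
- **Recruitment continues until the evaluable number is met** (section 11.1.4). So a re-routed patient costs time rather than sample size. Secondary-GF data may also inform dose decisions (section 12.2), and the combined endpoint counts these failures (section 7.1). This stands.

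**Conclusion.** The gap is real and cheap to close. As written, a patient who has not engrafted can be moved to weekly scheduled sampling and optional treatment. If treated, that patient is counted as secondary GF and left out of the All evaluable population. The next scheduled sample comes after 7 days (6–8) instead of 1–3. With a day-1 trigger, between none and six daily samples that could have prompted treatment are lost before the first weekly visit, depending on when ANC falls. Frequency cannot be derived, all analyses are exploratory (section 12.5), and the point does not call the trial into question.

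A reader might infer more than the documents support:

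- **That patients are denied emapalumab.** They are not; access continues at the same dose.
- **That 3.4.3 and 3.4.4 contradict each other.** One is a monitoring transition and the other a treatment-stopping rule. They are two standards with different purposes.
- **That all 15 samples missing after a day-1 trigger are lost chances to treat.** Only those after the fall below 500 are.
- **That interim decisions are biased in a known direction.** None can be derived. Guidance exists at 4 and 7 patients only, although an analysis at 10 is also planned.

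**What to change.** Amend section 3.4.3, with the matching tables and synopsis, in one of two ways:

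- **Confirm before moving.** ANC of 500 or more ends primary monitoring only after ANC has been below 500 and when three consecutive values confirm it. Use ANC alone, given the limited chimerism sampling below 30 kg. State what applies when the first such value comes on day 39 or 42, where fewer than two scheduled monitoring samples remain.
- **Or allow a return.** A patient whose ANC falls below 500 before that confirmation goes back to the primary-GF schedule and criteria until day 42. The existing reasons not to start treatment still apply. This needs few or no extra samples.

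Under either option, settle two further points:

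- **Label.** A patient treated on ANC below 500 plus CXCL9 above threshold before confirmed recovery counts as treated for primary GF and can be evaluable. A patient treated only on chimerism or platelet criteria counts as treated for secondary GF. Keep those criteria open from the first ANC of 500 or more, so that access is not delayed.
- **Patients who never fall below 500.** Set a fixed step-down day, for example day 21, the earliest day on which section 3.2 says GF is usually confirmed.

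**Cost.** A short amendment and about two extra ANC/CXCL9 samples per typical patient, mainly a burden in small children. A patient who never falls below 500 would have 6 + 7 = 13 scheduled samples on days 2–21 instead of 2 (days 8 and 15). Section 8.4 based its blood-volume estimate on a patient staying in each period for its maximum length, including 42 days of monitoring, so these samples are already allowed for.

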3.4.4 Treatment Period

Assessments to be performed during the treatment period are detailed in the Schedule of Assessments (Table 6a and Table 6b).

Criteria to enter treatment during the monitoring and extended monitoring period, and not to start treatment, are defined in section 3.4.3.

- Patients treated for primary or secondary GF will receive emapalumab for maximum 15 infusions or until engraftment is confirmed.
- Engraftment is defined as ANC \geq 500 cells/ μ L for 3 consecutive measures and donor chimerism above 60% (for primary GF) or ANC \geq 500 cells/ μ L for 3 consecutive measures and 2 consecutive measures of donor chimerism above 60% or 7 days of platelets above 20000 cells/ μ L without transfusion (for secondary GF).
- Preferably, ANC recovery should be based upon three consecutive laboratory values (ANC sample drawn 1 or 2 days apart maximum).
- Patients must be hospitalized in case of active infections requiring IV antimicrobial therapy during treatment.
- If engraftment is confirmed prior to the last dosing day (dose 15) or if patients discontinue treatment, patients will perform all assessments as per end of treatment visit (EoT) and can be discharged if hospitalized provided that there is no active infections requiring IV antimicrobial therapy.
- Patients who take prohibited medications will not be discontinued from emapalumab treatment unless for medical reasons.
- Pre-emptive treatment for secondary GF is optional and it is investigator's responsibility to decide whether to start pre-emptive treatment with emapalumab or not.

End of Treatment (EoT) visit

Assessments to be performed during the EoT visit are detailed in the Schedule of Assessments (Table 6a and Table 6b).

Patients who discontinue treatment or engraft before the last dosing day (dose 15) will attend the EoT visit. Patients who complete treatment until dose 15 will not be required to undergo an EoT visit.

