Patients with CXCL9 levels below threshold will be monitored and will enter follow up for non-emapalumab treated patients at the end of the monitoring periods. This additional group of patients will allow to confirm the frequency of GF when CXCL9 levels are below threshold.

In clinical practice, GF is usually not confirmed until at least day 21 and up to 42 days following HSCT, therefore the monitoring period for primary GF will last up to 42 days. As soon as an ANC is ≥ 500 cells/ μL , patients will enter the extended monitoring period for secondary GF which will last up to 98 days. ANC increase can occur within 10 days after HSCT, but may take up to 30-40 days, mostly depending on the source of stem cells. Secondary GF, which may occur after initial engraftment, is usually observed within the first few months after transplant, therefore the extended monitoring will last up to 98 days.

To achieve rapid IFN γ neutralization, an initial dose of 6 mg/kg emapalumab will be administered. To maintain further IFN γ neutralization covering the duration of engraftment, emapalumab administration will be continued at a dose of 3 mg/kg after 3 days (second infusion) and every 3 or 4 days thereafter until stable engraftment has been achieved or until a maximum of 15 doses. This definition of treatment duration will guarantee that patients are treated until the graft has clearly engrafted but not beyond. Further details on the dose regimen rationale can be found in section 5.3.

Patients treated pre-emptively for secondary graft failure will receive the same dose regimen as patients treated pre-emptively for primary graft failure in the 3 cohorts.

Patients will be followed up until 3 years post HSCT in order to collect survival data, occurrence of GvHD and use of defined treatments or procedures to support the graft function post-transplant.

Patients will be stratified at screening into two groups in order to include at least 40% malignant and 40% non-malignant. Stratification will allow to explore the appropriate dose inhibiting IFN γ production in a similar number of patients presenting malignant or non-malignant disease in each cohort. Patients below 1 year are considered more vulnerable and will therefore not be included in the study until the safety has been confirmed in patients 1 year or older.

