Assessments to be performed during the EoS visit are detailed in the Schedule of Assessments (Table 7a and Table 7b).

- For emapalumab treated patients, the EoS visit correspond to the last follow-up visit (Follow-up visit 6) at week 24 \pm 2 days from last study drug administration.
- Non-emapalumab treated patients will require to attend the EoS visit within 1 week from the last day in the monitoring periods.

Table 2 Transition between periods in case of ANC < 500 cells/ μ L during the monitoring period

Monitoring	Treatment	Follow-up For emapalumab treated patients	Follow-up For non-emapalumab treated patients
CXCL9 above threshold + ANC <500 cells/ μ L 	Enter treatment period		Perform EoS visit and enter phone-calls follow-up period:
CXCL9 below threshold + ANC <500 cells/ μ L  Continue monitoring ✓ Unless a second HSCT is required ✓ As soon as ANC \geq 500, transition to extended monitoring Table 3		Enter follow-up period: ✓ Upon completion of treatment or engraftment during treatment, whichever comes first ✓ Upon premature treatment discontinuation for any reason	
 ✓ At the end of monitoring or ext monitoring period ✓ In case of re-occurrence of malignant disease, GvHD diagnosis, uncontrolled infection or clinical manifestations of infections representing exclusion criteria at time of treatment ✓ If a second HSCT is required ✓ If any prohibited med is taken during the monitoring periods

Table 3 Transition between periods in case of ANC \geq 500 cells/ μ L during the monitoring period

Monitoring	Extended Monitoring	Treatment	Follow-up For emapalumab treated patients	Follow-up For non-emapalumab treated patients
As soon as ANC \geq 500 cells/ μ L during monitoring, enter extended monitoring	CXCL9 above threshold + Signs of sGF 	Enter treatment period	Enter follow-up period: ✓ Upon completion of treatment or engraftment during treatment, whichever comes first	Perform EoS visit and enter phone-calls follow-up period: ✓ At the end of monitoring or ext monitoring period ✓ In case of re-occurrence of malignant disease, GvHD diagnosis, uncontrolled infection or clinical manifestations of infections representing exclusion criteria at time of treatment
	If CXCL9 below threshold Continue extended monitoring unless a second HSCT is required		✓ Upon premature treatment discontinuation for any reason	
 ✓ If a second HSCT is required ✓ If any prohibited med is taken during the monitoring periods

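### For secondary graft failure, a patient can meet an entry sign and the engraftment definition that ends treatment on the same values, and that definition states neither its and/or grouping nor its time origin

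*Combined protocol and SAP*

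**What the plan says.** **Entry (Section 3.4.3; signs repeated in the synopsis and Sections 3.1 and 3.2).** In extended monitoring, treatment for secondary GF needs CXCL9 above threshold, the investigator's choice to treat, and a sign of secondary GF. The signs are "donor chimerism drop of at least 10% for 2 consecutive measurements and/or ANC below 500" cells/μL "and/or thrombocytopenia below 30000"/μL, with no explanation other than possible graft rejection. The sentence does not make clear whether that last qualifier covers all three signs or only the platelet one.

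**End (Section 3.4.4).** "Patients treated for primary or secondary GF will receive emapalumab for maximum 15 infusions or until engraftment is confirmed". For secondary GF, engraftment is ANC of at least 500 on three consecutive measures and "2 consecutive measures of donor chimerism above 60% or 7 days of platelets above 20000" cells/μL without transfusion. The synopsis and Table 1 footnote 5 repeat this. None of the three places groups the and/or terms or says from when the values count. CXCL9 is not part of the definition.

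**Related text.** Tables 2 and 3 in Section 3.4.5 move a patient to follow-up "Upon completion of treatment or engraftment during treatment, whichever comes first". Sections 3.2 and 5.3 speak of stable engraftment, and Section 3.2 adds: "This definition of treatment duration will guarantee that patients are treated until the graft has clearly engrafted but not beyond".

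**The concern.** A rule that starts treatment and a rule that ends it should not both be satisfied by one unchanged set of values. If they are, the duration of treatment depends on how each site reads the sentence and on when samples happen to be drawn, and not on what the graft does.

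What is at stake is the number of infusions, and so the exposure, in patients treated for secondary GF. Section 12.1 allows for about as many of them per cohort as are treated for primary GF. Sections 3.2 and 12.2 say their data may be used in dose decisions. Section 12.4 places them in the all-treated population and, with one post-dose PK sample, in the PK/PD population. Section 12.5 reports results separately for primary and secondary GF. If engraftment is ever summarised with this definition, status at entry could be counted as an outcome.

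**Working it through.** The plan gives no figure to reproduce here, so the check sets the two rules side by side.

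**1. Do the rules overlap?** Let ANC3 be ANC of at least 500 on three measures, CHIM2 be chimerism above 60% on two, and PLT7 be platelets above 20000 for 7 untransfused days. Two groupings are possible:

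- Reading A: (ANC3 and CHIM2) or PLT7
- Reading B: ANC3 and (CHIM2 or PLT7)

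For steady profiles (platelets untransfused):

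| ANC | Chimerism | Platelets | Entry sign present | A | B |
|---|---|---|---|---|---|
| 1000 | 95% to 85%, twice | 15000 | chimerism, platelets | met | met |
| 1000 | 50%, flat | 25000 | platelets | met | met |
| 1000 | 95%, flat | 15000 | platelets | met | met |
| 300 | 95%, flat | 50000 | ANC | met | not met |
| 300 | 95%, flat | 15000 | ANC, platelets | not met | not met |

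The chimerism and platelet signs can each coexist with engraftment under both readings. The ANC sign does so only under A, where the platelet clause stands alone. The last row shows that the overlap is not universal.

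**2. How wide is it?**

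- Platelet sign against platelet clause: above 20000 and below 30000.
- Chimerism sign against chimerism clause: Section 3.4.3 does not say whether the 10% is in percentage points or relative. In points, start − 10 > 60 gives any start above 70%. If relative, 0.9 × start > 60 gives any start above 66.7%. From 95%, drops of 10 to just under 35 points qualify (95 − 60 = 35).

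**3. Does any text fix the time origin?** The wording in Tables 2 and 3 and the references to stable engraftment point to on-treatment values but do not say so. Section 3.4.4 also states: "Preferably, ANC recovery should be based upon three consecutive laboratory values (ANC sample drawn 1 or 2 days apart maximum"). This is a preference about spacing and does not settle the start. Neither schedule delivers it: before treatment, "During the extended monitoring, CXCL9 and ANC measurements will be performed weekly up to day 98", and on treatment Table 6a samples every 3 or 4 days. Even if only values after TD0 count, nothing has to change from entry: chimerism that holds at 80% satisfies the chimerism clause.

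**4. When could an unchanged graft meet the end rule?** Take patients of 30 kg or more, Table 6a samples after TD0, and cohort 1 dosing (Section 5.4). For n ≥ 2, dose n falls between TD 3 + 3(n − 2) and TD 3 + 4(n − 2). Cumulative dose = 6 + 3(n − 1) mg/kg.

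| Dose | Treatment day | Cumulative mg/kg |
|---|---|---|
| 1 | 0 | 6 |
| 5 | 12-15 | 18 |
| 7 | 18-23 | 24 |
| 15 | 42-55 | 48 |

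- ANC: doses 2, 3 (in the differential) and 4, so three values exist by dose 4 (TD9-11).
- Platelets: scheduled only with hematology, at odd doses. The first two values after TD0 are at doses 3 and 5, which lie 6 to 8 days apart. The platelet clause is therefore documented at dose 5 at the earliest. TD12 counts both end days; where the gap is only 6 days and seven elapsed days are required, it waits for dose 7.
- Chimerism: first two scheduled values at doses 5 and 7, so dose 7.
- If values before TD0 count, the definition can already be met at dose 1.

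**The case against.** The strongest reply is that treatment is pre-emptive. Entry tests a change, with CXCL9 raised, and the end rule tests a level. A graft whose chimerism stops falling and holds at 80% may be what the sponsor means by engrafted, and Section 5.3 wants prolonged administration limited. Nothing in the protocol requires the entry sign to reverse. This stands to the extent that the review cannot call either rule clinically wrong. It does not remove the overlap, because the text never says that holding steady is the intended criterion.

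Second, a reader might infer that patients could be stopped at or just after the first dose. That needs values from before TD0 to count. The wording in Tables 2 and 3 and the references to stable engraftment argue against it, and it would make entry self-cancelling. On scheduled later values the earliest point is dose 5. Extra platelet counts taken outside the schedule could show seven days sooner, but Table 6a does not provide for them.

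Third, the qualifier about other explanations, the CXCL9 requirement and the investigator's choice all narrow who enters. That is correct; none of them separates the two sets of values.

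Fourth, the statistical consequence is limited. No endpoint in Section 7 is stated to use this definition, and secondary-GF data enter dose decisions on the ground of similar PK/PD. This also stands. The effect that can be shown is on treatment duration and exposure.

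**Conclusion.** The point holds as an internal conflict between the secondary-GF entry signs and the engraftment definition, compounded by an unstated grouping and time origin. It should be corrected, but it does not threaten the main result.

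Size: in cohort 1, for a patient of 30 kg or more with no change since entry, treatment could end at dose 5 (18 mg/kg) or dose 7 (24 mg/kg) instead of running to dose 15 (48 mg/kg). It could end at dose 1 (6 mg/kg) only if earlier values count. These figures assume scheduled samples only and no missed doses. The documents do not give the frequency, and secondary-GF treatment is optional.

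Two stronger inferences are not supported. The main efficacy endpoint, the evaluable population and the rules at 4 and 7 patients concern primary GF and do not use this definition. Nor can inflation of the event-free engraftment endpoint be claimed, because the text does not say how that endpoint defines engraftment. Section 12.5 defers detail to the SAP, and the text available here contains no SAP wording that resolves the grouping.

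**What to change.** **Protocol.** Reconcile the secondary-GF signs (Section 3.4.3, synopsis, Sections 3.1 and 3.2) with the engraftment definition (Section 3.4.4, synopsis, Table 1 footnote 5). State the and/or grouping, and state whether only values after TD0 count. The thresholds and the clinical rule are for the sponsor, and none is proposed here.

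**SAP.** Flag secondary-GF patients who already meet the reconciled definition on their last values before TD0, with a not-derivable category where data are missing. Show the flag and the number of doses received wherever secondary-GF data are summarised for engraftment or used for the dose decision. If the wording is left unresolved, derive the flag under both readings.

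**Cost.** Wording changes and one derivation. Table 6a has no chimerism at dose 1, so the flag must use the last two extended-monitoring values. Table 5a schedules chimerism and hematology at those visits. Below 30 kg, Table 5b leaves chimerism to clinical indication and, as it reads, schedules no hematology in extended monitoring, so some patients will be not derivable. If a secondary-GF engraftment count is reported, it may be lower.
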